1.0 Objectives / Specific Aims

The goal of this Stage 1 treatment study is to develop, systematically refine, and clinically evaluate a depression-specific Brief Behavioral Activation (BA) for adolescent vaping cessation mobile app (“VapeX”).

Aim 1: Develop and refine VapeX. Individual interviews with end-users (n=10) will inform the design of VapeX.

Aim 2: Via a two-arm pilot randomized controlled trial (N=106, randomized 1:1), examine the feasibility and efficacy of 1) VapeX vs. 2) treatment as usual. Subsequent iterative usability testing (n=5, or until saturation) will guide app refinements. Main outcomes, which will be assessed across 4-weeks of follow-up, include: 1) treatment feasibility, 2) treatment acceptability, 3) change in depression over time as a function of treatment, and 4) changes in vaping behavior (e-cigarette use episodes per day, days using an e-cigarette per week, number/duration of quit attempts, 7-day point prevalence abstinence at Week 4, use of other tobacco products) as a function of treatment.

2.0 Background

Nicotine Vaping is an Epidemic among Adolescents. The prevalence of vaping nicotine (i.e., e-cigarette use) has skyrocketed among adolescents in recent years¹⁻³, rising from near zero in 2011 to 27.8% in 2019⁴. These rapid increases in adolescent vaping led the Surgeon General in 2018 to declare adolescent e-cigarette use an epidemic⁵. High rates of vaping among adolescents are concerning because: 1) vaping carries a variety of short-term health risks⁶⁻⁸, with largely unknown long-term risks, 2) nicotine is highly addictive⁹, and 3) adolescents who vape are three times more likely to initiate combustible cigarette use¹⁰⁻¹⁴.

Adolescents who Vape are Interested in Quitting, but Interventions are Limited. Nearly half of all adolescents who vape are seriously interested in quitting, as our group reported in *JAMA Pediatrics*¹⁵. Yet, vaping quit attempts are often unsuccessful: one quarter of current vapers have made a quit attempt in the past year that resulted in relapse¹⁵. Despite high interest in quitting, extant cessation interventions have received little empirical investigation and no NIH-funded trials have examined the efficacy of interventions for adolescent vaping cessation. FDA-approved medications for adult nicotine dependence are not approved for adolescent use¹⁶. Instead, clinical guidelines¹⁷ and systematic reviews^{18,19} conclude that behavioral/psychosocial counseling is the first-line treatment approach for adolescent nicotine dependence. As such, there is clear need to develop, evaluate, and disseminate evidence-based psychosocial interventions for adolescent vaping cessation.

An Appropriate Intervention Must Target Established Vaping Risk Factors. Depressive symptoms, which are common among adolescent vapers (36%)²⁰, have recently been identified as a predominant vaping-related risk factor. Similar to the general population of adolescents who vape, 46.8% of adolescent vapers with depressive symptoms report seriously thinking about quitting¹⁵. Consistent with the transdiagnostic emotional vulnerability framework²¹, the relationship between depression and vaping is bidirectional such that depressive symptoms prospectively predict vaping initiation, and sustained e-cigarette use exacerbates depression²². This aligns with decades of research documenting depression as a robust risk factor for initiation of combustible tobacco use among adolescents^{21,23,24}, transition to regular smoking^{25,26}, difficulties quitting²⁷⁻²⁹, and relapse³⁰⁻³³.

Among cigarette smokers with depressive symptoms, tailored interventions that target both depression and tobacco use are necessary for cessation^{34,35}. Thus, an ideal candidate treatment for adolescent vapers with depressive symptoms likely must also target depressed mood. Brief Behavioral Activation (BA) is a well-established, evidence-based treatment for depression³⁶⁻³⁹ that has demonstrated promise for smoking cessation among adults⁴⁰ and adolescents⁴¹. Brief BA focuses on regular self-monitoring to 1) examine

already occurring activities and 2) facilitate the incorporation of new activities consistent with individualized values/goals across life areas. Completing enjoyable, important activities improves mood, making it easier to initiate and sustain cessation⁴⁰. An adapted version of Brief BA for adolescent vaping cessation could offer a promising approach to simultaneously target depressive symptoms in the service of promoting vaping cessation.

Summary of Scientific Premise. Nicotine vaping among adolescents is an epidemic. Adolescents want to quit vaping, but available treatment approaches within primary care, where youth are likely to receive treatment, are limited both in scope and in evidence base. To maximize efficacy and reach, a product that will fill this gap must: 1) directly target established risk factors for adolescent vaping and 2) be accessible via platforms already utilized by adolescents. The goal of this Stage 1 treatment study is to develop, systematically refine, and preliminarily evaluate a depression-specific Brief BA for adolescent vaping cessation mobile app (“VapeX”). This will build upon our team’s prior and ongoing research developing mobile app adaptations of Brief BA for depression and smoking cessation treatment within primary care⁴²⁻⁴⁵.

3.0 Intervention to be studied

VapeX. Features identified via individual interviews will form the basis of VapeX development. VapeX will be developed for iOS and Android, will be HIPAA-compliant, and will retain all key elements of Brief BA and standard cessation treatment in Goal2Quit (our team’s Brief BA for smoking cessation app), though these features will be modified based on individual interviews.

Brief BA components include: 1) Psychoeducation highlighting the connection between mood and vaping, 2) Identification of values and activities across life areas including relationships, responsibilities, recreation, education/career, health, and being vape-free, 3) Activity planning, and 4) Tracking mood and vaping. *Standard cessation components include:* 1) Reinforcement and support for quitting, 2) Interactive questions to identify past quit attempts and contributors to relapse, 3) Setting a quit date, suggested to be no later than two weeks after treatment initiation, and 4) Identification of triggers and development of coping strategies.

TAU. TAU is designed to mimic existing vaping cessation standard treatment. Participants in both conditions will be provided educational material about depression and vaping available via the National Cancer Institute’s Smokefree Teen website with a suggestion to discuss questions with their PCP. Across conditions, participants will not be precluded from obtaining additional treatment, which will be tracked as an outcome.

4.0 Study Endpoints (if applicable)

Primary outcome variables include:

Depression. The PHQ-8 will be used for preliminary screening and the PHQ-9 will be administered at final screening. Across all timepoints depressive symptoms will also be assessed via the Beck Depression Inventory-II (BDI-II). The BDI-II is a validated assessment of depressive symptoms among adolescents and is our primary depression outcome. Self-report and Electronic Health Record (EHR) data will be used to categorize concurrent depression treatment (therapy, medications) at baseline and across the trial.

Vaping. Nicotine vaping and quit outcomes will be assessed at each follow-up using a Timeline Followback for the last 6-months at baseline and since prior follow-up for each subsequent assessment. Frequency of vaping will be assessed in multiple ways including number of vaping episodes per day and number of days per week vaping. Use of other tobacco products and frequency of use will also be assessed. Cessation outcomes include: 1) number of quit attempts since last assessment, 2) duration of each quit attempt, 3) point-prevalence abstinence, and 4) continuous abstinence. E-cigarette dependence

will be assessed at baseline via the 10-item Penn State Electronic Cigarette Dependence Index (ECDI). Participants will report motivation to quit and confidence in quitting using a modified Contemplation Ladder.

Treatment Utilization. VapeX utilization will be tracked via analytics data. Specifically, we will examine 1) number of app sessions, 2) average time per session, and 3) total time using the app. Additionally, we will assess engagement with each individual component of the app. Analytics will be examined within each week and across the entire trial duration.

VapeX Feasibility and Acceptability. VapeX participants will self-report feasibility and acceptability at all follow-ups. As in our prior trials, participants will report: 1) ease of app use, 2) continued desire to use the app, 3) perceived benefits of using the app, and 4) suggested improvements.

Assessment Grid

	Screening	Baseline	Week 1	Week 2	Week 3	Week 4
Screening Questionnaire	x					
PHQ-8	x					
Demographics		x				
PHQ-9		x				
BDI-II		x	x	x	x	x
Current use of Psych Meds		x	x	x	x	x
TLFB		x	x	x	x	x
Cessation outcomes		x	x	x	x	x
ECDI		x	x	x	x	x
Contemplation Ladder		x	x	x	x	x
Tech Comfort		x				
Feasibility/Acceptability			x	x	x	x
VapeX Usability Scale			x	x	x	x
VapeX Utilization			x	x	x	x

5.0 Inclusion and Exclusion Criteria/ Study Population

Inclusion criteria:

- age 16-20
- vaped nicotine on ≥ 20 days out of the last 30⁴⁶
- elevated depressive symptoms, defined as a score of ≥ 10 on Patient Health Questionnaire-8 (PHQ-8) during preliminary screening and the Patient Health Questionnaire-9 (PHQ-9)⁴⁷ at final eligibility during baseline
- currently own an iOS or Android smartphone
- report willingness to utilize an app for quitting vaping nicotine (response of “yes” on yes/no item)
- have a valid e-mail address that is checked regularly or regular access to text messages (for follow-up assessments)
- has been seen (in person or remotely) by a primary care physician within the last year

Exclusion criteria:

- smoked cigarettes or used other tobacco products on ≥ 9 days out of the last 30⁴⁸⁻⁵⁰
- severe visual impairment
- currently receiving treatment for vaping or tobacco use
- current suicidal ideation, defined as a response ≥ 2 on item 9 of the BDI-II at baseline (See Protection of Human Subjects for comprehensive plans to address suicidality and clinical deterioration)
- household member currently enrolled in the study
- inability to read the consent form

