6.0 Number of Subjects

We will recruit up to 10 participants for individual interviews and 106 for the RCT, the first 5 of the RCT will be for usability testing.

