Identified patients will be sent an electronic communication (e-mail or message via the EHR patient portal, based on patient preferences) from a member of the study team inviting them to participate in a study. This electronic communication will include a link to complete study screening via REDCap. Within South Carolina, the legal age to consent to medical treatment is 16. At age 16, all MUSC patients can receive their own patient portal account and parents/guardians can be appointed as proxies. If participants do not respond to this invitation within 72-hours, we will contact them via phone, e-mail, and/or text-message (based on preferences within the EHR) to ensure they received the message. If interested, participants will complete an eligibility screening via MyChart/REDCap. This eligibility screening will assess: age, sex, e-mail access, English fluency, smartphone ownership, nicotine vaping status, willingness to use a mobile app for nicotine vaping cessation, and depressive symptoms via the PHQ-8. This eligibility screening will be used solely for screening purposes, not for research purposes. Within our informed consent documents, if a participant provides informed consent to participate in the study, they will agree that their screening information can be used for research purposes. After completing determination of eligibility, a member of the research team will complete remote electronic informed consent with the participant (see details below).

Recruitment may also occur in the following ways:

- 1) In Clinic: Participants may be recruited in clinic after being identified as a nicotine vaper by research personnel listed on this application.
- 2) Via advertisements (e.g., flyers) and online postings such as Craigslist.
- 3) Snowball recruitment: Enrolled participants can refer others to the study. If they refer someone that enrolls, they will receive additional compensation.
- 4) Recruiting parents with children who vape directly using IRB approved advertisements on online platforms.

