10.0 Study Design / Methods

Aim 1: Develop and Refine VapeX.

VapeX Development Testing

VapeX development will take place in three steps: 1) semi-structured individual interviews with end-users (n=10) and 2) software development. Individual interviews will follow standard procedures⁵¹. Individual interviews (1hr each, \$40 compensation in electronic gift card codes (e.g., Amazon) emailed to participants) will be divided into four parts: 1) discussion of apps for positive health behavior change and participants' experiences with such apps, 2) narrowed focus on mobile apps for quitting vaping and managing low mood, 3) even narrower focus on an initial version of the VapeX app, which will be previewed for the participant during the interview, and 4) discussion of features that participants would like included in VapeX that are not currently included. This discussion will begin with facilitators presenting participants with a list of features that have been included in other mobile app interventions for adolescent substance use treatment (**Table 1**)^{52,53}. Individual interviews may occur either remotely using an MUSC-approved HIPAA compliant video conferencing platform (e.g., Microsoft Teams) or in person, depending on the status of the COVID-19 pandemic.

Features identified via individual interviews will form the basis of VapeX development. VapeX will be developed for iOS and Android, will be HIPAA-compliant, and will retain all key elements of Brief BA and standard cessation treatment in Goal2Quit, though these features will be modified based on individual interviews. Brief BA components include: 1) Psychoeducation highlighting the connection between mood and vaping, 2) Identification of values and activities across life areas including relationships, responsibilities, recreation, education/career, health, and being vape-free, 3) Activity planning, and 4) Tracking mood and vaping. Standard cessation components include: 1) Reinforcement and support for

Table 1: App Features to Consider for VapeX

Domain	Specific Potential Features
Gamification	Rewards earned for continued app use or decreased vaping; Competitions within the app
Social Interaction	In-app communication with peers; Ability to help others quit vaping/provide peer support
Family Involvement	Resources for discussing depressed mood and/or substance use with parents
Dual Use	Psychoeducation about dual use and strategies to quit smoking while quitting vaping

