This R41 application consists of a 2-Aim proposal. In Aim 1, targeted end-users, defined as adolescent (ages 16-20) regular nicotine vapers (vaped on ≥ 20 days out of the last 30⁴⁶) with elevated depressive symptoms (score of ≥ 10 on the PHQ-9⁴⁷) who have been seen at least once in the last year by a PCP, will be recruited for individual interviews (n=10) that will inform the development of VapeX. In Aim 2, we will conduct a two-arm pilot feasibility randomized controlled trial (N=106; 1:1 randomization) with the first 5 participants recruited for usability testing and randomized to receive the VapeX app, to examine the feasibility and acceptability of VapeX as well as treatment efficacy for depression and nicotine vaping cessation relative to TAU.

Trial Management

The study will be managed from the Addiction Sciences Division within the Department of Psychiatry and Behavioral Sciences at the Medical University of South Carolina (MUSC). Recruitment, data collection, data management, and treatment provision will be coordinated and centrally managed at our research lab at MUSC and will be implemented within local Family Medicine/Primary Care clinics that are part of MUSC's Primary Care ICCE.

Data Management and Analysis

Participants will enter data in REDCap, a secure, web-based application designed exclusively to support data capture for research studies. REDCap provides: 1) an intuitive interface for data entry (with data validation); 2) audit trails for tracking data manipulation and export procedures; 3) automated export procedures for seamless data downloads to common statistical packages (SPSS, SAS, Stata, R); 4) procedures for importing data from external sources; and 5) advanced features, such as branching logic and calculated fields. These procedures are effective in minimizing data entry errors (e.g., missing or errant

data). All data from VapeX will be stored on a HIPAA-compliant server. Data analytic plans are outlined above.

Quality Assurance

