
Protections Against Risk

The recruitment project is stored in REDCap and only study team members will have access to the recruitment project database. The research team will only have access to the REDCap recruitment project while actively enrolling for the study. The recruitment project will be stored separately from the project containing research data. The recruitment REDCap project will potentially contain both identifiers and health information in the same project. All screening information will be kept in a password protected REDCap database. Only key study personnel will have access to the database. If an individual is not eligible to participate, his/her screener will include his/her first name and last initial and the reason for disqualification. Eligible participants' full name, telephone number and e-mail address will be recorded in the database. This is the only place where participants' names and subject identification numbers appear together. Eligible participants will be assigned a subject number, will complete informed consent (see procedures above), will be randomized (Aim 2), will complete baseline assessments, and subsequently will receive their randomized intervention (or will complete focus group Aim 1).

Upon completing eligibility screening, if study eligible, individuals will be provided with a verbal overview of the study, asked to review a consent form, and asked to provide informed consent (or assent, if under the age of 18). Participants will be informed of limitations of confidentiality (i.e., abuse or neglect, intention to harm self or someone else) both verbally and in writing during the informed consent process. The consent form will include the participant's name, but not his/her subject number. Consent forms will be provided in English. As utilization of VapeX requires that participants are able to read, participants unable to read the consent form on their own will not be included.

Regarding questionnaire data, data will be obtained for research purposes only. All data will be collected, stored, and managed via REDCap, which is a secure, web-based application designed exclusively to support

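### As worded, the eligibility criteria let Aim 1 interviewees and housemates of people who have finished the VapeX arm be randomised, which can dilute the comparison with TAU and bias acceptability ratings

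*Combined protocol and SAP*

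**What the plan says.** Section 5.0 contains one exclusion about contact with other participants: "household member currently enrolled in the study". A second exclusion touches on exposure to treatment: "currently receiving treatment for vaping or tobacco use". No criterion mentions Aim 1 participation, earlier enrolment in the RCT, or past access to VapeX.

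The Summary of the Protocol in Section 12.0 describes Aim 1 end-users as "defined as adolescent (ages 16-20) regular nicotine vapers" with elevated PHQ-9 scores and a primary care visit within a year. They "will be recruited for individual interviews (n=10) that will inform the development of VapeX". This is essentially the RCT population. Section 10.0 (Aim 1) gives each interview an "even narrower focus on an initial version of the VapeX app, which will be previewed for the participant during the interview", followed by a discussion of features to add. Section 3.0 makes the interview findings the foundation of the app.

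On whether the two samples may overlap, Section 6.0 says only "We will recruit up to 10 participants for individual interviews and 106 for the RCT". Section 13.0 (Protections Against Risk) describes eligible people who are randomised, assessed "and subsequently will receive their randomized intervention (or will complete focus group Aim 1").

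Section 8.0 adds a further channel: "Enrolled participants can refer others to the study". Section 10.0 pays $40 for a referral that leads to enrolment. No rule covers the allocation or analysis of people linked in this way.

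**The concern.** RCT participation lasts about 4 weeks. If enrolment ends at Week 4, a sibling or roommate of a former VapeX user then becomes eligible and may be allocated to TAU. The documents do not say that app access ends. Separately, an interviewee who has seen the app and suggested features for it meets the same entry definition and is not barred.

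Two results could be affected. TAU participants who already know VapeX content can narrow the between-arm difference, and Section 11.0 says the pilot is meant to estimate effect sizes for a larger project. Former interviewees in the VapeX arm would be rating an app they helped design, which can bias the acceptability ratings.

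The assessment grid in Section 4.0 has no item asking TAU participants about VapeX. Exposure that is not prevented at entry would therefore be hard to identify later.

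**Working it through.** **Does any text close the two routes?**

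- *Separate counts in Section 6.0.* These give two recruitment totals. They do not say that a person counted in one cannot be counted in the other.
- *The either/or wording in Section 13.0.* This describes workflow after eligibility is settled. It suggests separate samples but is not an eligibility rule.
- *The exclusion for current vaping treatment.* At most this covers someone using VapeX now. It does not reach a past preview, or a housemate who only saw the app.
- *Staff-issued download codes (Section 10.0).* These limit installation. Single use and expiry are not stated, and a code does not undo content already seen.

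Neither route is closed.

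**How large could the interviewee route be?**

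The plan gives no figure for contamination, and no alpha, power, effect size or SD for the comparison with TAU. There is nothing of its own to reproduce.

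Inputs from the documents: up to 10 interviewees (Section 6.0); 98 randomised 1:1 (Section 10.0); 49 per arm (Section 11.0, Sample Size Estimation).

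Assumptions, not in the documents: all 10 interviewees are randomised; a preview conveys a fraction r of the VapeX effect d; interviewees in the VapeX arm gain nothing extra from having seen it.

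- Expected number per arm: 10 / 2 = 5.
- Exposed share of TAU: c = 5 / 49 = 10.2%.
- Observed difference = d × (1 − c × r).

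To express this as power, take a true effect of 0.566 SD. That gives 80% power at 49 per arm, two-sided 0.05, and is a yardstick only. The Phase II column is 1 / (1 − c × r)², because sample size scales with 1/effect².

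| r | Shrinkage c × r | Power (from 80%) | Phase II sample size multiplier |
|---|---|---|---|
| 0.25 | 0.102 × 0.25 = 2.6% | 78% | 1.05 |
| 0.50 | 0.102 × 0.50 = 5.1% | 76% | 1.11 |
| 1.00 | 0.102 × 1.00 = 10.2% | 71% | 1.24 |

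With fewer interviewees the shrinkage falls in proportion.

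**Housemates and referred friends.** The documents give no count. Each TAU participant who received the full effect would remove 1 / 49 = 2.0% of the difference; nothing more can be computed.

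**Acceptability.** Only VapeX participants rate the app, so 5 former interviewees would be 5 / 49 = 10.2% of the randomised raters. The plan defines no acceptability proportion or threshold, so the size of any bias cannot be calculated.

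**The case against.** The strongest reply is that this is a drafting gap with little practical weight. A preview of an early version in one part of a one-hour interview is far from the intervention, which Section 10.0 describes as daily use of 5 to 10 minutes with planning and tracking. At most 10 people are involved, and randomisation spreads them over both arms. They must still meet the vaping and depression thresholds at entry, and the depression models adjust for baseline depression. Personal logins and tracking of additional treatment in both arms give further protection. No section states the purpose of the household rule or defines when enrolment ends. Contact between acquaintances is a general limit of individually randomised behavioural trials.

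Most of this stands as an argument about size. It does not show that either group is excluded.

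Stronger readings that a reader might infer are not supported:

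- *That dilution and inflated ratings will occur.* The documents give no overlap, exposure or effect figures. An interviewee whose suggestions were not adopted might rate the app lower, so even the direction of bias is open.
- *That 10.2% is the expected loss.* It requires every interviewee to be randomised and a preview to equal the full app.
- *That acceptability could be pushed past the 70% benchmark.* In Section 11.0 that benchmark applies to retention, measured by weekly app use. Acceptability is only summarised descriptively.
- *That a paid referral is itself prior exposure.* The payment depends on enrolment, not on ratings. The issue there is contact across arms, since about half of randomised referrer-referee pairs would be split under 1:1 allocation.

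**Conclusion.** The concern holds in a limited form. The criteria as written admit Aim 1 interviewees and housemates of people who have finished the VapeX arm, and no other text closes those routes. This can dilute the comparison with TAU and can bias acceptability ratings.

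The effect is probably small. With all 10 interviewees randomised, the loss runs from 2.6% at a quarter of the effect to an upper bound of 10.2%, and the low end is more plausible for a preview. The housemate and referral routes cannot be sized from the documents. The case for acting rests on how cheaply an avoidable source of contamination and rater bias can be removed, not on a demonstrated threat to the results.

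**What to change.** In Section 5.0, replace the household criterion with the following, marked as applying to entry to the RCT: *took part in an Aim 1 interview, was previously enrolled in the RCT, or has a household member who is or has been enrolled in the RCT*.

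For referrals (Sections 8.0 and 10.0), record each referrer-referee link. In Section 11.0, prespecify a sensitivity analysis that excludes TAU participants linked to a VapeX user. It should supplement the analysis of all randomised participants, because removing people from one arm departs from the randomised comparison. Postponing referrals until the referrer's Week 4 is not recommended: the referrer would by then have had the full app, a friend allocated to TAU would be no better protected, and recruitment would slow.

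Cost: at most 10 interviewees and a few housemates lost from the recruitment pool, one linkage field, and one additional analysis. No stated sample size changes.
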